6.1. ALL PATIENTS ENROLLED SET [ENR]

The all patients enrolled set (ENR) will include all patients who signed informed consent form (ICF) for this study.

6.2. SAFETY ANALYSIS SET (SAS) – (ALL TREATED POPULATION)

This analysis set includes all patients who have received at least one dose of surufatinib. Safety data will be evaluated based on this analysis set outcome. Patients in the SAS will be analyzed by their actual dose initially received. If patients have dose reduction during the study, all data will be summarized/ analyzed based on the initial dose of study medication received.

All safety analyses except for DLT summaries will be based on the SAS. Efficacy endpoints PFS and OS (OS applies to BTC and STS cohorts only) will be analyzed based on this analysis set.

6.3. DOSING LIMITING TOXICITY (DLT) EVALUABLE SET

The DLT set comprises all SAS patients who are evaluable for DLT assessment. DLT evaluable patients can be identified via answers to the question “DLT evaluable patients” on CRF “DLT Assessment” page.

DLT set (and summaries of DLTs) only applies to dose escalation phase patients.

A DLT evaluable patient has to meet the following criteria, which will not be confirmed via programming:

- Has not received any preventive treatment during the DLT period; AND
- Has completed the first 28-day treatment cycle with complete safety evaluations and has received at least 75% of the assigned surufatinib dose; OR
- Has a confirmed DLT during the first 28-day treatment cycle.

6.4. EFFICACY ANALYSIS SET (EAS)

This analysis set includes all patients who have received at least one dose of surufatinib and have had at least one

CCI

post-baseline tumor assessment.

All efficacy endpoints will be analyzed based on this analysis set except for analysis of PFS and OS, which will be analyzed based on the SAS. The OS analysis will be performed for the BTC and STS cohorts only.

6.5. PROTOCOL DEVIATION

Major protocol deviations related to study inclusion or exclusion criteria, conduct of the trial, patient management, or patient assessment will be listed for SAS.

The study team will discuss, identify and classify the important eligibility criteria or post-entry deviations from operational team monitor reports before final data base lock.

7. GENERAL CONSIDERATIONS

7.1. REFERENCE START DATE, REFERENCE END DATE AND STUDY DAY

Reference start date is defined as the date of the first administration of study medication. Study day will be calculated from the reference start date and will be used to show start/stop day of the assessments and events relative to the first administration of study medication.

Reference end date will be defined as the day of the last administration of study medication within the patient's last treatment cycle.

Study day (Day 1 is the day of the first administration of study medication) will appear in each listing where an assessment date or event date appears.

If the date of the event is on or after the reference start date then:

$$\text{Study day} = (\text{date of event} - \text{reference start date}) + 1.$$

[figure not shown]
If the date of the event is prior to the reference start date then:

$$\text{Study day} = (\text{date of event} - \text{reference start date}).$$

In the situation where the event date is partial or missing, the date will appear partial or missing in the listings, Study day, and any corresponding durations will be presented based on the imputations specified in Section 8.2.

In addition to the overall reference start and end date, the start and end of treatment within each cycle will be identified based on the data collected on the eCRF form and will be used when assigning events or assessments to a particular treatment cycle.

CCI

7.2. BASELINE

Unless otherwise specified, baseline is defined as the last non-missing measurement taken prior to reference start date (including unscheduled assessments). In case where the last non-missing measurement and the reference start date coincide, that measurement will be considered as baseline, but AEs and medications commencing on the reference start date will be considered post-baseline, that is, treatment-emergent or concomitant ("worst case" approach).

7.3. END OF TREATMENT

End of treatment reasons and treatment discontinuation date are captured on CRF page "End of Treatment". Patients who complete or prematurely discontinue the study medication need to return to the study site for a follow-up within 30 ± 7 days after the last dose of surufatinib. Measurements obtained during this visit will be considered as the 'End of Treatment' assessment.

7.3.1. End of Study

A patient is considered to have completed the study once he or she has completed the last visit, or the last scheduled procedure as outlined in the Schedule of Events in Protocol Appendix 1.

7.4. RETESTS, UNSCHEDULED VISITS AND EARLY TERMINATION DATA

In general, for by-visit summaries, data recorded at the nominal visit will be presented. Unscheduled measurements will not be included in by-visit summaries. Unscheduled measurements will contribute to worst-case summaries. In the case of a retest (visit-specific unscheduled visit number assigned), the latest non-missing measurement among all scheduled and unscheduled measurements for that visit will be used for by-visit summaries.

Early termination data of patients prematurely discontinued from study medication will be presented together with the end of treatment assessment for study medication completers.

By-patient listings will include scheduled, unscheduled, retest, and early discontinuation data.

7.5. VISIT WINDOWS CONVENTIONS

Unless otherwise indicated, in the treatment period, during Cycle 1 and Cycle 2, the visit window will be ± 1 day. From Cycle 3 onward, the visit window will be ± 3 days. In the follow-up visit, the visit window is ± 7 days. All data will be organized and analyzed according to the scheduled times as outlined in the protocol and by the visit

CCI

denoted on the Case Report Form (CRF).

7.6. STATISTICAL TESTS

There is no formal statistical hypothesis testing in this study. The confidence intervals will be 95%, unless otherwise specified in the description of the analyses.

7.7. COMMON CALCULATIONS

For quantitative measurements, change from Baseline will be calculated as:

- Change from baseline = Test Value at Visit X – Baseline Value
- Percentage change from baseline = $[(\text{Test Value at Visit X} - \text{Baseline Value}) / \text{Baseline Value}] * 100$

The time from Date of Event A to Date of Event B (years) is calculated as:

- $(\text{Date of Event B} - \text{Date of Event A} + 1) / 365.25$.

The time from Date of Event A to Date of Event B (months) is calculated as:

- $(\text{Date of Event B} - \text{Date of Event A} + 1) / 30.4375$.

7.8. SOFTWARE VERSION

All analyses will be conducted using SAS® Version 9.4 or higher.

8. STATISTICAL CONSIDERATIONS

8.1. MULTICENTER STUDIES

This study will be conducted by multiple investigators at approximately 8-15 sites. No adjustment in aspect of site effect will be performed. Data from all centers will be pooled prior to analysis.

8.2. MISSING DATA

Generally, the missing efficacy and safety data will not be imputed except for the critical missing and incomplete dates which will be handled as described in this section.

CCI

For partially missing dates, the Age (Years), Duration of malignancy (years) and Duration of metastasis (years) will be based on imputed values. For all calculation elements, if the date part is missing while year and month present, 15th of the month will be used for imputation. If both date and month part are missing while year presents, July 1st will be used for imputation.

When no imaging/measurement was done at all at a particular time point, the patient is not evaluable at that time-point. If only a subset of lesion measurements were made at an assessment, usually the case is also considered not evaluable at that timepoint, unless a convincing argument can be made that the contribution of the individual missing lesion(s) would not change the assigned time point response.

For ORR and DCR calculation, patients with missing responses will be considered non-responders, thus contribute only to the denominator.

Initial Diagnosis Date

If year and month are known but the day is unknown, day will be imputed as 15. If only year is known, month and day will be imputed to July 1st. If the diagnosis date is completely missing or the year part is unknown, the diagnosis date will not be imputed. The imputed date will be compared to reference start date. If it is later than the reference start date, the incomplete date will be imputed as the reference start date.

Adverse Events Date

For adverse event, incomplete start dates and/or stop dates will be imputed. Start date will be imputed first when the start date and stop date are both incomplete for a patient. If the field of year is missing, then no value will be imputed. The following rules will be applied to impute the incomplete start date, assuming year is available.

Missing or incomplete start date

In case the start date of an AE is completely missing, or year part is unknown, the start date of AE will not be imputed.

In case the start date of AE is in the same year as reference start date (when only year is recorded), or the start date is in the same month and year (if only the day is missing) as the reference start date, then the start date of the AE will be imputed by the minimum of the reference start date and the AE resolution date. In all other cases the available year and month are not equal to the corresponding year and month of the reference start date or the available year is not equal to the corresponding year of the reference start date, the missing start day will be imputed by the 1st day of the month and the missing start month will be replaced by January.

In the case only the month is missing while year and day are recorded, then both day and month will be considered as missing. If the year part of start date of an AE occurs in the same year as reference start date, then the start date of

the AE will be imputed by the minimum of the reference start date and the AE resolution date. If an AE is observed on different year of the reference start date, January 1st will be used to complete the start date of the AE..

Missing or incomplete end date

Incomplete end dates will be imputed to the last possible date. In the case the year and month are known, AE end date will be imputed as the last day of the month. In the case if only the year is known, AE end date will be imputed as the December 31st of the year. If the imputed AE end date is after the death date, then the date of the death will be imputed as the AE end date. If the end date is completely missing or the year part is unknown, the end date will not be imputed. If the imputed end date is before the start date (imputed or non-imputed start date), then the stop date will be imputed using start date.

For AE events continuing at the cut-off date, the end date will not be imputed and will be reported as "ongoing".

Medications/Procedures Date

There will be no imputation for complete missing start date or end date of medications/procedures.

Impose incomplete start date as earliest possible date, i.e. first day of month if day unknown or 1st January if day and month are unknown.

Impose end date as latest possible date, i.e. last day of month if day unknown or 31st December if day and month are unknown, if not resulting in a date later than the date of patient's death. In the latter case the date of the death will be used to impose the incomplete stop date.

Above rules will be applied for prior/ concomitant medications/ procedures and prior oncology therapies.

Duration will not be calculated in case either the start date or end date is completely missing, but it will be calculated based on the imputed start/ end date if either the start date or end date is incomplete.

[figure not shown]
Last Tumor Assessment Date

If year and month are known but the day is unknown, day will be imputed as the first day of the month. If only year is known or a date is completely missing, the date will not be imputed. If the date of death is complete, the imputed date will be compared with the death date, the earlier date will be used for the date of last tumor assessment.

Subsequent Anti-tumor Therapy Date

When an incomplete subsequent anti-tumor therapy start date is reported, every effort will be made to identify the precedence relationship of starting date of subsequent anti-tumor therapy relative to the reference end date and the date of disease progression (if happened). Generally, records of subsequent therapy should all start after EOT/ PD.

CCI

	Condition	Reference end date (D1)	Date of earliest disease progression (D2)	Imputed start date for anti-tumor therapy
Known part or clinical evidence to show precedence relationship	1	Before	Before	Minimum (D1, D2) -1
	2	After	After	Maximum (D1, D2) +1
	3	Before	After	D2+1
	4	After	Before	D2-1
	5	No or not applicable	Before	D2-1
	6	No or not applicable	After or others	D2+1
	7	Before	No or not applicable	D1-1
	8	After or others	No or not applicable	D1+1

For example, condition 3, if the known part of the anti-tumor therapy indication that the anti-tumor therapy starts before reference end date but after date of disease progression, then incomplete start date of anti-tumor therapy will be imputed as one day posterior to date of disease progression.

If the imputed start date is later than date of death, then the imputed start date will be further imputed to date of death.

Death Date

If year and month of death date are known but the day is unknown, day will be imputed as 15. If only year is known, month and day will be imputed to July 1st. There are two exceptions of the below two scenarios:

- If the imputed death date is prior to the last known alive date, then the death date will be imputed to the next day of last known alive date.
- If the imputed death date is after end of study date with the year and month are the same as end of study date, then the death date will be imputed to the date of end of study.

9. OUTPUT PRESENTATIONS

Appendix 1 details the conventions for presentation of data in outputs.

The templates provided with this SAP describe the presentations for this study and therefore the format and content of the summary tables, figures and listings to be provided by IQVIA Biostatistics.

Continuous variables will be summarized using descriptive statistics, i.e., number of patients(n), mean, median, standard deviation (SD), and ranges (minimum, maximum).

Qualitative variables will be summarized by count(s) and percentages (%). Unless otherwise stated, the calculation of percentages will be based on the total number of included in the relevant analysis set.

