17. SAFETY OUTCOMES

All outputs for safety outcomes except DLT summary will be based on the SAS. Safety data will be summarized by dose cohort in escalation phase and disease cohort in dose expansion phase.

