17.3. ECG EVALUATIONS

The 12-Lead Electrocardiogram (ECG) will be performed at screening, and on Days 1 and 15 in Cycle 1, when ECG data will be collected at pre-dose and at 2 hours +15 minutes post-dose (around C_{max} after single dose and at steady state in order to evaluate concentration-QT relationship for surufatinib). The ECG values at C1D1 pre-dose will be used as 'baseline' value in the analysis. ECG will also be conducted on Day 1 of each cycle from Cycle 2 and onward, as well as the treatment completion visit.

For each time-point, following measurements with change from baseline values will be presented for the SAS:

- Heart rate (bpm)
- RR (ms)
- PR (ms)
- QRS (ms)
- QT (ms)
- QT correction by Bazett (ms)
- QT correction by Fridericia (ms)
- Overall ECG interpretation
 - Abnormal, clinically significant (CS)
 - Abnormal, not clinically significant (NCS)
 - Normal
 - Incomplete analysis
 - Uninterpretable
 - Not applicable

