17.3.3. Analysis of QTc Change from Baseline (Δ QTc)

The change from baseline in QTcF (Δ QTcF) intervals will be evaluated as follows:

- Δ QTcF at each time point will be listed for each patient and treatment. For each time point of measurement, Δ QTcF will be summarized using descriptive statistics (mean, SD, median, min, max).
- The incidence of patients with Δ QTcF increase >30 to 60 msec and >60 msec will be summarized.
- The incidence of patients with Δ QTcF increase >30 to 60 msec and >60 msec by time-point in Cycle 1 will also be summarized.
- Patients with Δ QTcF increase >60 msec will be listed.
- Mean Δ QTcF versus time profile for each dose group will be plotted on the same graph.

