17.6. OTHER SAFETY ASSESSMENTS

17.6.1. ECOG Performance Status

The Eastern Cooperative Oncology Group (ECOG) Performance Status will be summarized descriptively by visit and a shift table will be also summarized from the “ECOG Performance Status” CRF page. In addition, the summary descriptive table by visit will include specific ECOG grades and binary grouping grades (0-1, 2-5). The shift table will be summarized from baseline to worst post-baseline.

Details about ECOG performance status scores can be found in Protocol Appendix B.

[figure not shown]
A listing of ECOG Performance Status will be provided.

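### By-visit ECOG and ECG-interpretation percentages default to the whole treated set as denominator, so as written they fall as patients leave

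*SAP*

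**What the plan says.** SAP section 9 gives the general rule: "Unless otherwise stated, the calculation of percentages will be based on the total number of included in the relevant analysis set". For safety, SAP section 17 names the set: "All outputs for safety outcomes except DLT summary will be based on the SAS". SAP 6.2 defines it: "This analysis set includes all patients who have received at least one dose of surufatinib". The denominator is therefore fixed once dosing has started.

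Two by-visit categorical summaries fall under that rule:

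- **ECOG (SAP 17.6.1):** "the summary descriptive table by visit will include specific ECOG grades and binary grouping grades (0-1, 2-5", with no denominator given.
- **Overall ECG interpretation (SAP 17.3):** "For each time-point, following measurements with change from baseline values will be presented for the SAS". The list that follows includes the categorical overall interpretation. The schedule has no upper limit: "ECG will also be conducted on Day 1 of each cycle from Cycle 2 and onward".

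Three other provisions bear on the point. SAP 8.2 says that missing safety data are in general not imputed. SAP 7.4 builds by-visit summaries from data recorded at the nominal visit. Protocol section 10 says that analyses use observed data unless a method for missing data has been specified.

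**The concern.** A patient can be counted in an ECOG grade or ECG category at a visit only if assessed at that visit. Someone who has progressed, died or stopped treatment has no value there, and none is imputed. That patient nevertheless stays in the denominator.

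A whole-set denominator suits a cumulative quantity such as the incidence of treatment-emergent adverse events (TEAEs), and SAP 17.1.1 states it expressly for that purpose. A by-visit percentage is a prevalence among those seen, and dividing by everyone ever treated mixes that prevalence with retention. The abnormal percentage then drops over successive cycles even when the condition of the assessed patients has not changed, and it drops fastest in the arm that loses patients fastest. For a safety abnormality the error runs in the reassuring direction.

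The 12-lead ECG is a named secondary safety endpoint of the expansion phase (Protocol 4.2.4, SAP 3.2.2). ECOG status is not on that list.

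**Working it through.** **1. Does anything in the text override the default?** SAP 17.1.1 (TEAEs), 16.1.3 (ORR) and 16.1.4 (DCR) each state their own denominator. SAP 17.3 and 17.6.1 do not. SAP 4.4, which records departures from the protocol's analysis, mentions only added ECG analyses and no departure from the observed-data principle. So the default applies to both tables.

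**2. Formula.** Let N be the SAS count in the column, a the number assessed at the visit, x the number of those in a given category, and f = a/N.

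Printed % = 100·x/N = (100·x/a) × (a/N) = (% among assessed) × f

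The relative understatement is 1 − f, the same for every category. The categories together sum to 100f%, not 100%.

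**3. Worked case (illustrative).** Take Arm A with N = 30 and a = 12, so f = 0.40, and x = 3 at ECOG 2 or worse. Among assessed: 3/12 = 25%. As printed: 3/30 = 10%, which is 25% × 0.40.

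**4. How small could f be?** The plan prints no by-visit percentage to reproduce and no retention by visit. As an assumed stand-in for f, I take the planning PFS rates in Protocol 10.1. The rationale is that treatment normally runs until progression (SAP 4.1.2). As a check that these inputs were read correctly, the binomial rules built on them reproduce the protocol's figures: 90.6% and 2.8% (30 patients, at least 9), 84.9% and 4.9% (15, at least 6), 83.3% and 7.0% (10, at least 3). This checks the reading of the inputs, not the proxy.

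| Arm and time | N | assumed f | mean number assessed | true 20% prints as | true 80% prints as |
|---|---|---|---|---|---|
| A (BTC), 16 weeks | 30 | 0.40 | 12.0 | 8.0% | 32.0% |
| A (BTC), 16 weeks | 30 | 0.15 | 4.5 | 3.0% | 12.0% |
| B or C (NET), 11 months | 15 | 0.50 | 7.5 | 10.0% | 40.0% |
| B or C (NET), 11 months | 15 | 0.19 | 2.85 | 3.8% | 15.2% |
| D (STS), 4 months | 55 | 0.40 | 22.0 | 8.0% | 32.0% |
| D (STS), 4 months | 55 | 0.10 | 5.5 | 2.0% | 8.0% |

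The Arm D rates are stated for each sarcoma subtype cohort and are applied here to the whole arm.

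**5. Shape over time.** For Arm A, assume exponential decline through 40% at week 16 (rate −ln 0.40/16 = 0.057 per week) and a constant 20% at ECOG 2 or worse among those assessed:

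| Week | Patients assessed | Prints as |
|---|---|---|
| 4 | 23.9 | 15.9% |
| 8 | 19.0 | 12.6% |
| 16 | 12.0 | 8.0% |
| 24 | 7.6 | 5.1% |
| 48 | 1.9 | 1.3% |

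The apparent improvement is entirely attrition. With the number assessed as denominator, every row reads 20%.

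**6. Where the effect does not reach.** SAP 17.3.3 limits by-time-point QTcF categories to the first cycle: "increase >30 to 60 msec and >60 msec by time-point in Cycle 1 will also be summarized". If 90% to 100% of patients have the Day 15 ECG (assumed), a true 10% prints as 9.0% to 10.0%.

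**The case against.** The strongest reply is that the default yields to anything stated otherwise, and that the same SAP section hands format and content to table templates, which are not in the text available here. By-visit denominators are often set in such templates, and Protocol section 10 already points to observed data. This stands in part: one cannot say that the tables will print the wrong figures. What can be said is that the written rule, followed literally, gives this result, and that the protocol sentence pulls the other way without the conflict being resolved.

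Second, the effect can be seen by a careful reader. SAP 9 requires counts beside percentages, grade counts should add up to the number assessed, and the ratio of abnormal to normal is unchanged. This is true, but it asks the reader to undo the table.

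Third, late deterioration is not hidden overall. The ECOG shift to worst post-baseline, notable ECG values by worst value, CTCAE shifts to worst grade and TEAE incidence are per-patient outputs that visit attrition does not erode in this way. ECG intervals are also summarised as continuous values. This stands and limits the consequence.

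A reader might also infer three stronger things that the documents do not support:

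- **QTcF-change categories shrink at later visits.** Their by-time-point percentages stop at Cycle 1. Later time points get only mean, SD, median and range, and the overall incidence is per patient.
- **The echocardiogram overall evaluation is affected in the same way.** SAP 17.6.2 presents values and changes by visit but says only that the overall evaluation is summarised separately, not that it is by visit.
- **Understatement of 50% to 90% is a finding about this trial.** That range is 1 − f under an assumed proxy. Treatment past progression is possible (Protocol 5.6) and would raise f; stopping without progression would lower it.

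**Conclusion.** The point holds for two tables: ECOG grades and the 0-1 versus 2-5 grouping by visit, and overall ECG interpretation by time-point. Under the written default, every percentage in them is the percentage among assessed patients multiplied by the fraction of the SAS still assessed. That relation is exact. Its numerical size is not known, because retention by visit is not in the documents; at an assumed 40% retention the printed figure is 40% of the observed one.

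The conclusion rests on the SAP text as it stands and would lapse if the templates already specify the number assessed. The consequence is confined to descriptive safety tables. No hypothesis is tested, and the primary PFS analysis is unaffected. It is still worth correcting, because the text departs from the protocol's observed-data principle and does so in the direction that makes abnormalities look rarer.

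**What to change.** Add to SAP section 9: *For categorical summaries by visit or time-point, the denominator is the number of patients in the analysis set with a non-missing assessment at that visit or time-point, and this number is shown in the table.* Then check that the ECOG and ECG-interpretation templates agree. Keep the SAS denominator for TEAE incidence.

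The cost is a sentence in the SAP, a template check and, if needed, a denominator change in two table programs. No new data are required. The drawback is that late-visit percentages will rest on small numbers and describe only patients still being assessed, so comparison across arms and over time remains limited. Showing the number assessed makes that limitation plain.
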